**13.07.2017**

## **Background**

Secondary lymphedema is one of the most severe complications resulting from damage to lymphatic drainage due to breast cancer treatment. Many women suffer from lymphedema after breast cancer treatment. Due to the lack of standard diagnostic criteria for the incidence of lymphedema varies from less than 5% to more than 50%. In a recent meta-analysis, it has been found to be 21.4%.

The primary risk factors of lymphedema are lymph node involvement and axillary lymph node dissection. The other risk factors are radiotherapy, adjuvant chemotherapy, early postoperative swelling, body mass index, advanced age, insufficient physical activity, infections in the affected arm and injuries. A study performed axillary dissection in women with breast cancer and found that 13.4% of the women not receiving radiotherapy and 42.4% of the women receiving radiotherapy had lymphedema.

Lymphedema reduces the quality of life due to physical and psychosocial disorders it creates. Women with lymphedema have physical problems such as restricted movements, retraction, weakness, pain and swelling on the affected breast and arm, difficulty in maintaining daily life activities and psychological problems like low self-confidence, disappointment, sadness and fear due to the appearance of lymphedema.

It has been reported that the yearly cost of treatment (visits to therapists and compression garment) per person is \$977 for lymphedema, \$277 for subclinical lymphedema, higher than \$1400 for moderate and severe lymphedema. Effective management of lymphedema on the affected arm could reduce negative effects of lymphedema and resultant high treatment costs.

Nurses believed that risk reduction (95%) and self-management (68%) were the responsibility of nursing while 69% felt that management of lymphedema was the responsibility of a different discipline, such as lymphedema therapy. The patient-centered educational and behavioral program delivered by trained nurses is effective to enhance lymphedema risk reduction. Lewis and Morgan emphasized that cooperation with public health nurses improves

patient care outcomes and costs associated with lymphedema management. At this point, the literature suggested that nurses should inform individuals about the risk of lymphedema after breast cancer.

It has been shown in the literature that women are not aware of lymphedema before its development, are unable to recognize its symptoms and can not take sufficient preventive measures. Similar to the aims of the present study, Zhou et al. examined effects of a comprehensive Health Belief Model (HBM) based nursing care program on the quality of life, lymphedema and other complications after breast surgery in their randomized controlled study on women in 2016.

The conceptual framework most frequently used to explain health behavior and to help patients to acquire this behavior is HBM. The model describes what motivates people to exhibit or not exhibit health behavior and especially what conditions are effective at this behaviors. The results of the present study, using HBM, will contribute to determination of beliefs and attitudes likely to create problems with adoption of behavior preventing lymphedema and selection of nursing interventions performed to manage the condition. Chronicity of lymphedema, likely to appear in the long-term, and its potential to affect the quality of life indicate that individuals with breast surgery have home care needs.

## **Study Protocol**

### **Aims**

The aim of this study was to examine effects of HBM based nursing interventions offered at home visits on lymphedema development in women undergoing breast surgery.

### **Study design and setting**

The study had a single-blind, randomized controlled experimental design. To avoid bias, the participants were not told whether they were in the experimental or the control group. The conceptual structure of the study is given in Figure. This randomized clinical trial was based on

the guidelines proposed by the Consolidated Standard of Reporting Trials – CONSORT 2010.

The study was conducted at homes of patients receiving treatment for breast cancer at a hospital and living in Samsun, a city in northern part of Turkey , between May 2016 and April 2017.

### **Inclusion criteria**

The study population included individuals receiving radiotherapy after breast surgery. Inclusion criteria were diagnosis of primary breast cancer and having stage I, II and III, having axillary dissection, not having the diagnosis of lymphedema, receiving radiotherapy, volunteering to participate in the study, age over 18 years and female and residing in the city.

### **Non-inclusion criteria and exclusion criteria**

Exclusion criteria were diagnosis of bilateral breast cancer, open wound or infection in the upper extremities, musculoskeletal disorders preventing movements of the upper extremities, ongoing adjuvant systemic chemotherapy.

### **Randomization**

An intervention group and a control group were formed by using the research randomizer software. The program used random numbers to select participants and randomly assign them to the experimental or control group (100 participants were assigned to each group). Homogeneity test showed no significant difference between the measures of the groups in Table 1 ( $p>.05$ ).

Blinding of data collectors and the statistician was implemented in this randomized blinded study. Another researcher who did not know the group assignments coded the data in the computer. After statistical analysis was conducted and the research report was written, the assistant researcher explained the codes for the experimental and control group. Therefore, blinding of data collectors, statistical analysis, and report writing was provided.

### **Study outcomes**

Personal Information Questionnaire;The questionnaire, developed by the researchers, is composed of 17 questions about sociodemographic characteristics, diagnosis and treatment of breast cancer, behavior of lymphedema prevention.

Quick-Disabilities of the Arm, Shoulder and Hand Score;Q-DASH is used to determine severities of disabilities in the upper extremities and benefits gained from treatment. It was adapted...by Duger et al. and its cronbach's alpha was reported to be .91. It is a five-point likert scale and includes 11 questions. The score zero indicates lack of a disability and 100 the most severe disability.

Strategies Used by Patients to Promote Health;SUPPH is a self-report scale created by Lev and Owen to evaluate self-efficacy of individuals in development of health promotion strategies. It was adapted by Akin and its Cronbach's alpha was reported to be .92. The scale consists of 29 items. The subscale stress reduction includes the items 1-10, making decision the items 11-13, positive attitude the items 14. Each item is scored from one to five:one corresponds to very little and five very much. The lowest and the highest scores for the scale are 29 and 145 respectively. Higher scores show higher levels of self-efficacy in self-care behavior 29.

European Organization for Research and Treatment of Cancer Quality of Life Scale for Breast Cancer 23;EORTC QLQ-BR23 was developed from European Organization for Research and Treatment of Cancer Quality of Life Scale 30 by EORTC to measure the quality of life in individuals with breast cancer. It was adapted Turkish by Demirci et al. The scale is composed of 23 items, a four-point scale and has two scales named FS and SS. Cronbach's alpha was reported to be .88 for the FS .66 for the SS. The FS has the subscales body image (items 39,40,41,42), sexual functions (items 44,45), sexual satisfaction (item 46), worry about the future (item 43). The SS has the subscales side effects of systematic treatment (items 31,32,33,34,36,37,38), breast symptoms (items 50,51,52,53), arm symptoms (items 47,48,49), worry about hair loss (item 35). The lowest and the highest scores for each scale are zero and

100 respectfully. Higher scores for the FS show a higher quality of life and higher scores for the SS indicate a poorer quality of life.

To calculate scores for the FS and the SS, the total score for the items of each scale is divided by the total number of items and the following formulae are used:  $FS = \{1 - (((\text{total score for the items}) / \text{number of items}) - 1) / \text{range}\} \times 100$  and  $SS = \{(((\text{total score for the items}) / \text{number of items}) - 1) / \text{range}\} \times 100$ . The highest and lowest score for the items are four and one and the difference between them, that is, three, refers to range.

Arm Circumference Measurement Form; The form was made on four different sites on both arms: at the dorsum of the hand, the wrist, and 10cm below and above of the elbow. The difference more than 2cm between circumferences of the arms was considered as significant in terms of lymphedema.

### **Protocol**

Oral informed consent was obtained from the eligible women at the initial interviews on the phone. The women who agreed to participate in the study were assigned to the groups according to the research randomizer software. The women assigned to experimental and control groups were planned first home visit and obtained written informed consent was obtained at this visits. At the Intervention group; the researcher made pretest (baseline measurements) before the nursing interventions at the first home visit. The researcher offered education and guide about prevention of lymphedema after the baseline measurements at the first home visit. Second and third home visits were made three and six months after the first visit. At the second and the third home visits, the measurements were repeated, and the nursing interventions were maintained in the direction of the patients' individual needs.

At the control group; the researcher administered the pretests at first home visit. The measurements were repeated in the third and sixth months after the first home visit. The

researcher also given at the end of the sixth month, all of the nursing interventions, given to the intervention group, for the control group.

### **Intervention**

Education Material; Breast Cancer Related Lymphedema Education Guide, prepared in light of the literature and revised in accordance with three experts opinions, was used at home visits. The content of the guide was directed towards supporting seriousness and sensitivity of the participants about lymphedema and created by taking account of HBM.

Home Visits; At the first home visits to the intervention group, the researcher met the participants and their families, explained the aim of the study and administered the pretests. The guide was introduced, and health education was given. Arm exercises used to prevent lymphedema were demonstrated and measurement of the arm circumference was taught. Follow-up forms were introduced and from the women were asked to do exercises as daily, make measurements as weekly, and record them in the forms day to day regularly. The arm measurements made by the researcher were included into the analysis. The participants and their families were encouraged to phone and receive counseling about things which they needed. Each home visit lasted 45 minutes on average. Three and six months after the first visit, the patients were phoned and made an appointment. At the second and the third home visits, the measurements were repeated, and the nursing interventions were maintained in the direction of the patients' individual needs (repeated of education, exercises and arm circumference measurement, control of follow-up forms).

At the first home visits in the control group, the researcher was introduced herself, explained the study and administered the pretests. The measurements were repeated in the third and sixth months after the first home visit. The women in the control group were not told about the nursing interventions, given to the intervention group, during the study period in order to

avoid bias. At the end of the sixth month, education and guide about prevention of lymphedema were offered to this group.

Reminders; In the intervention group was sent a message reminding behavior preventing lymphedema every week.

### **Sample size calculation**

Before initiation of the study, to achieve 80% power, 95% confidence interval and 0.05 error range, a power analysis was made with G-power software and the sample size was found to be 14 were in each groups. However, a higher number of participants was planned to be included into the study:37 formed the intervention group, 35 formed the control group. At the end of the study, a post-hoc power analysis was made by using primary outcome variables. The post-hoc power analysis score was .98 for Q-DASH, .94 for SUPPH, .67 for the function scale (FS) and .80 for the symptom scale (SS) in EORTC QLQ-BR23.

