### **Hypotheses of the study**

1. Extremity function restrictions will be lower in the intervention group than in the control group.
2. Self-efficacy levels will be higher in the intervention group than in the control group.
3. Functions improving the quality of life will be higher in the intervention group than in the control group.
4. There will be fewer symptoms reducing the quality of life in the intervention group than in the control group.
5. The incidence of lymphedema will be lower in the intervention group than in the control group.

6. The mean cost of the intervention group at home visits, will be lower than in the control group.

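### The stated aim is lymphedema development, but the only variables labelled primary leave out the protocol's own lymphedema measure

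*Combined protocol and SAP*

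**What the plan says.** The Aims section states a single purpose, to "examine effects of HBM based nursing interventions offered at home visits on lymphedema development in women undergoing breast surgery".

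The Study outcomes section describes the instruments without ranking them. It defines lymphedema from circumferences taken at four sites on both arms: "The difference more than 2cm between circumferences of the arms was considered as significant in terms of lymphedema". The Protocol and Intervention sections have measurements at the first visit and at three and six months, and say that the researcher's arm measurements enter the analysis.

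The word primary is applied to outcomes once. In the Sample size calculation, "a post-hoc power analysis was made by using primary outcome variables", with values of .98 for Q-DASH, .94 for SUPPH, .67 for the BR23 function scale and .80 for the BR23 symptom scale.

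Hypotheses of the study lists six unranked hypotheses. The fifth is "The incidence of lymphedema will be lower in the intervention group than in the control group". For comparisons, the Statistical analysis plan names repeated-measures analyses of variance and t-tests only.

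**The concern.** The question in the aim and the variables labelled primary are different things. Of the four scores, "Q-DASH is used to determine severities of disabilities in the upper extremities", SUPPH concerns self-efficacy ("Higher scores show higher levels of self-efficacy in self-care behavior"), and the two BR23 scales concern quality of life. Trained women could report better function or confidence without any change in arm circumference. The plan has no rule saying which hypothesis decides success, so nothing in it stops the questionnaires from carrying a conclusion about lymphedema.

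The cost conclusion is exposed too. The Statistical analysis plan ties treatment cost to potential lymphedema incidence, and the closing text under Ethical aspects calls the practice cost-effective. That part rests on the outcome with the least statistical support in the plan.

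**Working it through.** **1. Outcome status, side by side**

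| Variable | Labelled primary | Power figure | Fitting test named |
|---|---|---|---|
| Q-DASH | yes | .98 | yes (ANOVA, t) |
| SUPPH | yes | .94 | yes |
| BR23 function scale | yes | .67 | yes |
| BR23 symptom scale | yes | .80 | yes |
| Inter-arm circumference difference | no | none | possible (ANOVA), not stated |
| Lymphedema by the 2 cm rule (hypothesis 5) | no | none | no |

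None of the four primary variables (0 of 4) is the protocol's lymphedema measure.

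**2. The plan's sample size.** It states 14 per group at 80% power and 0.05, without outcome, effect size, SD or sidedness, so it cannot be reproduced forward. Solving backwards for a comparison of two means:

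- Two-sided: d = (1.960 + 0.842) × √(2/14) = 1.06 (1.10 with the t distribution).
- One-sided: d = (1.645 + 0.842) × √(2/14) = 0.94 (0.97 with the t distribution).

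Read this way, the 14 refers to a difference of about one SD on an unnamed continuous variable. It gives no basis for incidence.

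**3. The post-hoc power figures.** For a two-sided t-test with 37 and 35 women, the noncentrality is d × √(37 × 35/72) = 4.24d. Powers of .98, .94, .67 and .80 correspond to d of about 0.96, 0.84, 0.57 and 0.67. They describe the questionnaires only.

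**4. What 35 control and 37 intervention women offer for incidence.** The control rates are the two in the Background: 21.4% overall and 42.4% with radiotherapy. The documents give no effect size, so relative risks of 0.50 and 0.25 are assumptions. The test is two-sided at 0.05:

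power = Φ[(p_C − p_I − 1.96·SE0)/SE1], where SE0 uses the pooled rate and SE1 the separate rates.

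For 42.4% against 21.2%, the pooled rate is (35 × 0.424 + 37 × 0.212)/72 = 0.315, SE0 = 0.1095 and SE1 = 0.1072. Power = Φ[(0.212 − 0.2147)/0.1072] = Φ(−0.025) = 49%.

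| Control rate | Assumed RR | Power | Power, Fisher exact | n per arm for 80% (continuity-corrected) |
|---|---|---|---|---|
| 42.4% | 0.50 | 49% | 44% | 75 (84) |
| 42.4% | 0.25 | 88% | 86% | 30 (36) |
| 21.4% | 0.50 | 24% | 20% | 184 (202) |
| 21.4% | 0.25 | 52% | 48% | 70 (82) |

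Setting power to 80% and solving for the intervention rate gives a required fall from 42.4% to about 13.3%, or from 21.4% to about 1.0%.

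The Randomization section gives 100 per group, against 37 and 35 in the Sample size calculation. These must be reconciled. At 100 per group every row but the third would reach 80%. The mismatch between aim and primary set does not depend on which figure is right.

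**The case against.** The strongest reply is that no section formally designates a primary outcome. The label comes from one retrospective power sentence, and the hypotheses carry no rank, so being fifth in a list is not a demotion. This stands as a limit: the ranking is inferred. It does not remove the problem, because if the label is set aside the plan has no primary outcome at all.

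Three stronger readings are tempting and not supported.

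- A reader might infer that the trial has no evidence on lymphedema. Circumference is measured at every visit and analysed, and incidence is a stated hypothesis. The gap is in status, power and test.
- A reader might infer that none of the four scores touches swelling. The BR23 symptom scale includes a three-item arm-symptoms subscale, 3 of the 15 items listed (7 + 4 + 3 + 1), whose wording is not given. What can be said is that none of the four is the circumference-based definition.
- A reader might infer that the 2 cm cut discards a calculable share of the sample. The plan does not say that circumference is analysed only as yes or no, and it gives no rule for combining four sites. The usual efficiency formula for one normal variable, φ(z)²/[p(1 − p)], runs from about 0.22 at 5% incidence to 0.64 at 50%, the span that the Background itself gives. No single loss figure is justified.

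It is also fair to say that the closing effect statement is confined to perceived barriers, benefits, self-efficacy and cost. It does not claim that the questionnaire scores show less swelling. The risk is one the plan leaves open, not one shown to have occurred there.

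**Conclusion.** The concern holds in this form: the aim names lymphedema development, the only variables labelled primary omit the protocol's lymphedema measure, and that measure has no power basis and no named test for its incidence. A positive result on the four scores would not answer the aim.

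On incidence, power with 35 and 37 women is 24% to 49% for an assumed halving and 52% to 88% for an assumed fall to a quarter. These ranges rest on assumed relative risks, a two-sided 0.05 test, complete follow-up, and background rates from other populations with unstated definitions and follow-up. They show that hypothesis 5 has no assured power; they do not predict its result. Power for a continuous circumference analysis cannot be computed, because no SD is given.

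**What to change.** The documents report post-hoc power and findings, so the data have been analysed. Promoting circumference to primary now would be outcome switching. It should be named primary only if results had not been seen.

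1. Restate the aim and conclusions so that claims from the four primary scores are limited to arm function, self-efficacy and quality of life.
2. Report lymphedema as a prespecified hypothesis, without primary status and without a power claim.
3. Add a between-group analysis of the inter-arm circumference difference at month 6 as a continuous measure, adjusted for its baseline value. State the site or the rule for combining sites, and label the analysis post hoc if it was not planned.
4. Report the 2 cm incidence beside it, with a test for proportions such as Fisher's exact test and a confidence interval for the difference.

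The cost is rewording plus two short analyses of measurements already taken; no new data are needed. The downside is that favourable questionnaire results no longer support a headline claim about lymphedema, and the interval for incidence may be wide.

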### **Statistical analysis plan**

Data obtained in this study were analyzed with SPSS 21.0. Multifactorial variance analysis of repeated measures was used to compare the groups in terms of dependent variables, the significance test of difference between two means to compare pretest and posttest measures, one-way variance analysis of repeated measures to compare intragroup pretest and posttest measures and t-test for dependent groups with Bonferroni correction to perform further analysis of the difference between the mean scores of the groups. Intention-to-treat (ITT) analysis was utilized to eliminate effects of dropouts from the study, to maintain randomization. To prevent bias the database were analyzed by a statistician who was independent of the study.

Costs of treatments likely to be given for lymphedema in the intervention group and the control group due to the potential incidence of this condition and HBM based nursing interventions to be offered at home visits were made. The costs of the nursing interventions included time spent by the researcher at home visits, transportation for these visits, reminders on the phone, education material and tape measure. The cost of treatment for lymphedema included costs of medical treatment of an individual with stage I/II lymphedema in upper extremities in hospital. It was based on opinions of three experts. To calculate the costs from the perspective of Social Security Institution, prices of services and materials reported in Health Services Bulletin issued in Mar 2017 were taken. The expenses directly made by the patients were determined by the mean value of prices obtained from three national firms.

[figure not shown]

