### **Ethical aspects**

Ethical approval was obtained from DEU Noninterventional Clinical Research Committee (Protocol number: 2014/08-19; approval number: 248; date: 4 April 2013 970-GOA) and State Hospitals Directorate. Oral informed consent was obtained from the women at the initial

interviews on the phone and written informed consent was obtained at the first home visits. At the end of the study, nursing interventions about prevention of lymphedema were offered to the control group.

In the current study, the HBM based nursing interventions offered at home visits decreased perceived barriers to lymphedema management, increased perceived benefits and improved self-efficacy in positive health behavior.

The cost of treatment for lymphedema in the intervention group was four times as low as that in the control group, which confirmed the sixth hypothesis. The finding indicated that follow-up of women having breast surgery through home visits is a cost-effective practice. Programs conducted in cooperation with public health nurses improve patient care outcomes and reduce costs for lymphedema. Sixty-seven percent of the women mention the presence of a financial burden of breast cancer treatment and 80% of the women point out to the cost of treatment for lymphedema. Treatment of breast cancer costs \$14.887-23.167 in patients developing lymphedema after breast surgery than those without lymphedema and this complication increases indirect costs due to loss of work force.

Abbreviations: EORTC QLQ-BR23, European Organization for Research and Treatment of Cancer Quality of Life Scale for Breast Cancer 23; SUPPH, Strategies Used by Patients to Promote Health; Q-DASH, Quick-Disabilities of the Arm, Shoulder and Hand Score.

**FIGURE** Consort flowchart

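### Four scores are treated as primary with no ranking and no error control across them; at two-sided 0.05 each, with any one enough for a claim, family-wise error is about 9% to 19%.

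*Combined protocol and SAP*

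**What the plan says.** The Sample size calculation section gives its design inputs as "80% power, 95% confidence interval and 0.05 error range". It names no outcome, effect size or sidedness. It then reports that "a post-hoc power analysis was made by using primary outcome variables" and gives one power value each for Q-DASH (.98), SUPPH (.94), BR23-FS (.67) and BR23-SS (.80). The term primary is plural, and no score is placed ahead of the others.

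The Hypotheses section lists six unranked statements. Numbers 1 to 4 correspond to the four scores, number 5 to lymphedema incidence and number 6 to cost.

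The Statistical analysis plan says: "Multifactorial variance analysis of repeated measures was used to compare the groups in terms of dependent variables". It gives no significance level for that analysis, no order of testing, no split of alpha and no rule for when the trial counts as positive. It does use Bonferroni, but only for dependent-groups t-tests that follow up differences in mean scores. No test is named for incidence, and cost is described only as a costing exercise.

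The Ethical aspects section also carries some discussion of results, and says of the cost result alone that it is one "which confirmed the sixth hypothesis".

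**The concern.** With four co-equal primary scores and no stated success rule, each score offers a separate opportunity to claim a positive trial. The Bonferroni step does not help here: it limits error among follow-up comparisons within a score, not the number of between-group claims made across scores. The stated aim does not single out a lead outcome either, because the Aims section speaks of lymphedema development, which is not among the four scores called primary.

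At stake is what a reader may conclude from one significant score out of four. If that score is taken as a confirmed primary hypothesis at the 5% level, the evidence is weaker than the label suggests.

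**Working it through.** **Inputs from the document**
- Error level 0.05, power 80%, group sizes 37 and 35, four primary scores: Sample size calculation.
- Hypotheses 1 to 4, each with a direction: Hypotheses of the study.

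**Inputs assumed**
- Each score has one deciding between-group test at two-sided 0.05. The plan states neither a test-level alpha nor sidedness.
- Any one significant score can be claimed.
- Correlations between the four test statistics are equal, with values 0, 0.3, 0.5, 0.7 and 0.9. The document gives none.

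**The plan's own figure.** The 14 per group cannot be reproduced, because no effect size, SD, outcome or test is given for it. This does not affect the point: family-wise error depends on the number of tests, their level and their correlation, not on the sample size.

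**Step 1. At least one false positive, either direction, independent tests**
1 − (1 − 0.05)^4 = 1 − 0.8145 = 0.185, or 18.5%.
Upper bound under any dependence: 4 × 0.05 = 20%.

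**Step 2. At least one false positive in the hypothesised direction, independent tests**
A two-sided 0.05 test rejects in one given direction with probability 0.025.
1 − (1 − 0.025)^4 = 1 − 0.9037 = 0.096, or 9.6%.

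**Step 3. Correlated tests.** Four equicorrelated standard normal statistics were simulated with no true effect, and draws with at least one value beyond 1.96 were counted.

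| Assumed correlation | Either direction | Hypothesised direction |
|---|---|---|
| 0 (exact) | 18.5% | 9.6% |
| 0.3 | 17.4% | 8.7% |
| 0.5 | 15.6% | 7.8% |
| 0.7 | 13.0% | 6.5% |
| 0.9 | 9.3% | 4.6% |

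The yardstick is 5% for the middle column and 2.5% for the right-hand column, since 2.5% is what a single two-sided 0.05 test allows in one direction. Relative to its yardstick, each column is inflated by a factor of about 1.9 to 3.9.

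**Step 4. Cost of a correction.** Holm over four tests compares the ordered p-values with 0.05/4 = 0.0125, 0.05/3 = 0.0167, 0.05/2 = 0.025 and 0.05. With 37 v 35, 80% power and a two-sided two-sample t-test (noncentral t, 70 degrees of freedom), the detectable standardised difference is:
- at 0.05: 0.67 SD
- at 0.0125, the strictest Holm step: 0.81 SD

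A normal approximation confirms the scale. √(1/37 + 1/35) = 0.236, so (1.960 + 0.842) × 0.236 = 0.66 and (2.498 + 0.842) × 0.236 = 0.79.

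**The case against.** The best defence is that the inflation is conditional. It needs a rule under which any one score suffices, and no such rule is written. If all four scores had to be significant, testing each at 0.05 would not inflate error at all. The 0.05 is a sample-size input rather than a claimed trial-wide rate. The hypotheses are directional, so the two-sided percentages overstate the chance of a false confirmation by about a factor of two.

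Most of this stands, and the figures are conditional for that reason. It does not remove the point. A plan that leaves the success rule open leaves the error rate open too, and the one hypothesis the document does call confirmed is claimed on its own, which does not fit an all-must-succeed rule.

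A second defence is that a correction would probably change little. If the post-hoc powers came from two-sided two-sample t-tests at 37 v 35, the implied p-values are about 0.0001 (Q-DASH), 0.0007 (SUPPH), 0.006 (SS) and 0.0175 (FS), and all four pass Holm over four. This is fair as an illustration, but the document does not say which test lay behind those powers and reports no outcome p-values.

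Three stronger readings are tempting and are not supported:
- **That six hypotheses are each tested at 5%.** No test-level alpha is stated, and hypotheses 5 and 6 have no named test. No six-test error rate can be attributed to the trial.
- **That the plan has no error control.** It applies Bonferroni to the follow-up t-tests. What is missing is control across scores.
- **That the FS result alone is fragile.** This needs the assumed t-tests above, a list of six tests, and hypotheses 5 and 6 both non-significant, although the document calls the sixth confirmed.

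**Conclusion.** The concern holds for the four scores. Following the plan as written leaves error across them uncontrolled, and the Bonferroni step does not reach that far. On the assumptions of two-sided 0.05 per score, one deciding test each and any one sufficient, family-wise error is 18.5% if the tests are independent and falls to about 9% at a correlation of 0.9. In the hypothesised direction the range is 9.6% down to about 5%. The correlations are assumed. The document does not show that any reported conclusion is wrong. This is a change that should be made, not a fault that invalidates the trial.

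**What to change.** In the Statistical analysis plan:

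1. Name one between-group contrast per score from the planned repeated-measures analysis, for example the group-by-time term, as the test that decides. No new time point or separate test is needed.
2. Declare the four contrasts (Q-DASH, SUPPH, BR23-FS, BR23-SS) as one family, tested with Holm at a total two-sided 5%.
3. Add hypotheses 5 and 6 to that list only if a test is named for each. Otherwise report them as estimates with 95% confidence intervals and do not describe them as confirmed.
4. If the rule is adopted after the results are known, label it post hoc. The document is dated July 2017, gives a study period ending April 2017 and already reports post-hoc power, so this label is likely to be needed.

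No new data are required. The cost is a stricter threshold, at most 0.0125 for the smallest p-value, which raises the detectable difference there from about 0.67 to 0.81 SD at 37 v 35; later Holm steps cost less. These group sizes come from the Sample size calculation section. The Randomization section instead says that "100 participants were assigned to each group", and the two statements need to be reconciled before a final figure is quoted.
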